4.4 Qualitative Data Analysis

Interviews and focus groups will be transcribed and then analysed. A thematic analysis will be employed to code the transcripts and identify emerging themes.⁸⁵ These themes will then undergo a further round of classifying, and will be sorted into high-level themes and sub-themes.

A thematic analysis is carried out across the interview and focus group data, following a three-stage process:

- 1. **Transcripts are coded by research questions within the following** four topics:
 - a. Reach
 - b. Engagement
 - c. Mechanisms of impact
 - d. Implementation and feasibility

This first stage is a 'low-inference and descriptive' process of data management.

- 2. Data is coded by themes that respond to the research questions: these themes are identified both deductively and inductively, using constructs from the literature when supported by evidence, and creating new constructs where it does not. When appropriate, we will also use the TDF to help categorise the themes to inform findings and adopt a contextualist method that takes into account the individual perspective, as well as the social context.
- 3. **Themes are refined:** this is achieved by reviewing their relation to each other, grouping them into conceptual categories where possible, and ensuring that they comprehensively cover the data.

The predetermined topics of the interview guide will be used to interrogate the data, maintaining a balance between deduction (using existing knowledge and the research questions to guide analysis) and induction (allowing concepts and ways of interpreting experience to emerge from the data).

Researcher bias will be mitigated by using the interrater reliability checker on NVIVO, ensuring that multiple researchers are coding transcripts in the same way for a sample of the transcripts. In the event of discrepancies, researchers will also meet to discuss any discrepancies and agree on a code-book. Verbatim participant quotations and case examples will be used to provide evidence and exemplify the theme(s) discussed in the paragraph before the quotation. Any quotations used will be selected by the qualitative researchers who conduct the data analysis on the basis of how well they exemplify the theme(s) discussed.

⁸⁵ This approach will follow an adapted version of Virginia Braun & Victoria Clarke (2006) Using thematic analysis in psychology, Qualitative Research in Psychology, 3:2, 77-101, DOI: 10.1191/1478088706qp063oa

6. Limitations and generalisability

The effect sizes of the impact evaluation will be specific to the financial incentives component of the app: As participants assigned to the control group will have an experience that is identical to that of users in the intervention groups, except for the financial incentives themselves, this trial won't generate evidence on the impact of the app alone or the impact of the app+financial incentives against no intervention. We believe that these questions are important, but outside the scope of this project.

The trial relies on participants accurately self-reporting their dietary behaviours, in addition to their weight at the baseline and each measurement time point. As a result, effect sizes estimated for dietary outcomes could be an overestimate of the true effect of offering financial incentives if participants in the intervention groups are more motivated to report good behaviours. This could be because of desirability bias, erratic eating habits (which make it harder for participants to recall what they have eaten accurately) or because they have an implicit motivation to pay more attention to what they eat (hence being more likely to overcome the typical under-reporting observed in food recall questionnaires). In addition, providing self-report data is effortful and may increase the risk of data attrition throughout the trial.

Providing control group participants with a wearable device and app-based measurements may itself improve their health behaviours through regular monitoring and feedback. This may lead to the evaluation underestimating the scheme's impact when compared to the true "business-as-usual". However, we are confident that this is a worthwhile trade-off as it enables the collection of objective, behavioural outcome metrics in a robust RCT design. It is also the only design which enables isolating the impact of incentives in the context of a digital scheme.

Offering participants 10 diet-related health challenges from which they could freely choose from might dilute the treatment effect across the dietary primary outcomes. The rationale for this limitation is that trying to change too many diet behaviours might then dilute the size of the impact on any of these behaviours. For instance, if all of the challenges were focussing on fruit and vegetables, we would have a narrower impact but might expect greater effects on this particular behaviour.

The trial will take place exclusively in Wolverhampton and might not generalise to other locations. Findings from the pilot can be extended to the other UK locations with high prevalence of low SES population under the assumption that (i) the advertisement campaign and the recruitment process in this pilot are representative of (or similar to) what would happen if they were launched at a national scale (ii) the population of Wolverhampton is representative of the low SES population of the UK (e.g. not more/less skewed towards a particular age group, or towards higher/lower

BMI) (iii) users in Wolverhampton respond to financial incentives similarly to how the average UK participant would.

7. Appendices

Appendix A - Alternatives to Intake24

	Method & description	Pros	Cons
Subjective measures (short time period)	STRONGLY RECOMMENDED Automated 24-hour dietary recall: Online questionnaires	Fewer errors; Quick & low burden for participants; Reduced burden for researchers; Cost-effective; Suitable for large studies; Easier to estimate portion size	Relies on accurate recall
	24-hour dietary recall : Open-ended questionnaires administered by a trained interviewer	Relatively quick & low burden; Procedure does not alter food intake; Sensitive to ethnicity-specific differences	Relies on accurate recall; Expensive due to high interviewer burden and data entry for paper-based survey; Coding and conversion of data to nutrients is time and labour intensive; Participants may change answers due to social desirability bias
Objective measures	Duplicate diet approach : Collection of duplicate diet sample and direct analysis	Objective (minimises self-report errors)	Expensive; High individual burden; Unsuitable for large-scale studies; Requires specialist laboratory equipment
	Food consumption record: Observation by trained staff	Objective (minimises self-report errors)	Expensive; Highly intensive for researchers; Limited to specific times and places; Observations may alter individuals usual eating patterns
Subjective measures (long time period)	Dietary history : Questionnaires administered by a trained interviewer about habitual food intake and dietary behaviours	Energy intake and most nutrients can be estimated reasonably accurately; Only 1 interview necessary	Relies on accurate recall; Data quality depends on interviewer skills; May be difficult for those with erratic eating habits Coding and conversion of data to nutrients is time and labour intensive; Participants may change answers due to social desirability
	Food frequency questionnaire: Self- or interviewer- administered questionnaire about the	Low burden; Easy and flexible to administer; Low cost;	Relies on accurate recall; Not comprehensive to all food consumed; Food list may not be reflective of

frequency with which food	
items or groups are	
consumed over set period	

Appendix B - Additional information on power calculations

All calculations have been carried out with the statistical software R version 4.1.0, using the packages "tidyverse", "pwr", and "data.table", "ggplot2".

Allocation ratio across arms

To answer the primary research question, comparisons will be made between all incentive arms (pooled) and the control arm. To optimise power in such a scenario, we have assumed *unequal allocation* of participants to the control and intervention arms at the analysis, such that, with 3 intervention arms, for every 1 participant in each intervention arm there will be 3 participants in the control arm.⁸⁶

Individual or household-level randomisation?

Randomising participants at the individual level or at the household level (i.e. clustered) is a key trial design decision which has implications for both statistical power and the estimation of treatment effects (due to the risk of spillover effects).

With individual-level randomisation, spillover could arise because individuals within a household that are assigned to different trial arms can influence each other's outcomes (e.g. a household member in the intervention arm can encourage another member in the control arm to do more PA). This can lead to underestimation of the treatment effect. Household-level randomisation minimises the risk of within-household spillover effects because all household members are assigned to the same arm.

With household-level randomisation, it is also important to consider that household members have outcomes that are likely to be non-independent or correlated (e.g. families tend to be active together), and therefore each individual contributes less information to the analysis.⁸⁷ The extent of this non-independence or correlation is quantified using the *intra-cluster correlation* (ICC).

The extent to which clustering at the household level affects statistical power depends on the ICC and the sizes of clusters (households) in the trial. In the current trial, cluster size depends on the household sizes signing up to the trial, and on the proportion of people within each household that sign up to the trial. Therefore, there are three key questions that should be answered:

⁸⁶ Torgerson, D. (2008). *Designing randomised trials in health, education and the social sciences: an introduction*. Springer. Chapter 10, pp. 108-113.

⁸⁷ This is a distinct issue from spillover risk, but both aspects arise from the same underlying issue: household members are not entirely independent in their behaviour and their outcomes.

- What is the intra-cluster correlation (ICC) within households for the PA and dietary outcomes? We estimate that intra-cluster correlation is sizable, especially for diet it could range from 0.2 to 0.5, with this assumption guided by estimates from prior literature.⁸⁸ Higher ICCs indicate a stronger association of behaviours among household members. We believe that an ICC of 0.2-0.4 could be realistic for this trial as published estimates based on the Health Survey for England data show an ICC of 0.26 for households, for a binary variable of "moderately/vigorously active in sports"; it also shows ICCs of 0.33 and 0.53 for the binary variables "eats fruit at least 1/day" and "eats vegetables at least 1/day", respectively.⁸⁹
- Within each household, what is the proportion of people that are expected to sign up? We assume that if a person within a household signs up, then all the other adults in the household will sign up too (conservative assumption). There is no available data on the proportion of adults within a household that are likely to sign up to the trial, and whether this varies by household size (e.g. whether within 2-person households, on average 2 adults are likely to sign up, whether in 3-person households only 1 adult is likely to sign up...etc.). Therefore, currently we assume that all adults within a household will sign up; this is a conservative assumption as it increases the required household sample size, owing to the need for cluster-randomisation.
- What is the distribution of household sizes that are expected to sign up? We estimate that 60% of trial participants could be in the same household with at least another trial participant (conservative assumption). There is no available data on the household sizes that are likely to sign up to the trial (i.e. whether the recruitment campaign will somehow be biased towards small or large households). Therefore, we assume that the household sampling will be random, guided by the distribution of household sizes in Wolverhampton. To obtain an estimate of this distribution, we used Census 2011 data on the distribution of household size (including children) in Wolverhampton⁹⁰. The average household size (including children) in Wolverhampton is 2.4 people; the table below shows the distribution of the number of adults per household and proportion of the total number of households (102,177 households in total).⁹¹ For example, in a sample of 1000 participants, we assume that 39% will come from single-person households

⁸⁸ A Danish study estimated an ICC of 0.07 for accelerometer-measured MVPA among families with children (Petersen et al. 2020). Estimates based on the Health Survey for England data (1994) show an ICC of 0.26 for households, for a binary variable of "moderately/vigorously active in sports"; it also shows ICCs of 0.33 and 0.53 for the binary variables "eats fruits at least 1/day" and "eats vegetables at least 1/day", respectively (Gulliford et al. 1999).

⁸⁹ Gulliford et al. 1999. Health Survey for England data refer to 1994.

⁹⁰ https://www.ukcensusdata.com/wolverhampton-e08000031#sthash.0ov8DqvG.dpbs

⁹¹ Various observations suggest that household size in the trial may be on the lower end: Children in larger households are less likely to have high BMI (Dasgupta & Solomon, 2018); children of single-parent households are at a higher risk of obesity (Duriancik & Goff, 2019); the proportion of people who are inactive/overweight increases with age (https://commonslibrary.parliament.uk/research-briefings/sn03336/) while average household size is higher for those 30-49 years old, and then decreases (ONS 2019).

(389 people), 41% will come from households with two adults (409 people across ~204 households), 20% will come from households with at least three adults (202 people across ~67 households).

Table 25. Distribution of the number of adults per household in Wolverhampton (Census 2011 data).

Adults per household	Number of households	% of total (102,177 households)		
1	39,777	39%		
2	41,784	41%		
3+ *	20,616	20%		
* set to 3 for simplicity in estimations as Census 2011 data does not provide further granularity				

* set to 3 for simplicity in estimations as Census 2011 data does not provide further granularity

Adjusting for multiple comparisons

For the primary outcomes, we will adjust for multiple comparisons using the Benjamini-Hochberg procedure within the physical activity outcomes (2 comparisons) and dietary outcomes (4 comparisons) separately. For the exploratory outcomes and questions, we will adjust for multiple comparisons separately within each research question and separately for physical activity and dietary outcomes. For example, when examining effects after 1 month on the primary outcomes, we will perform 2 comparisons for the physical activity outcomes and 4 for the dietary outcomes. We will do the same for the analysis at 3 months.

Baseline measures and other covariates

We assume that the inclusion of covariates such as baseline calorie intake, baseline MVPA min/day, socio-demographic information, and anthropometric information will reduce variance in the outcome measures, and therefore increase power. Based on prior research, the pre-post correlation in the calorie intake measure using Intake24 is expected to be ~0.5; for the measure of MPVA min/day this is expected to be ~0.8.⁹² Therefore, we conservatively assume that a correlation coefficient of at least 0.5 is realistic in this trial.⁹³

⁹² https://www.ncbi.nlm.nih.gov/pmc/articles/PMC6722486/;

https://journals.humankinetics.com/view/journals/jpah/8/5/article-p668.xml

⁹³ Note that our estimates are additionally conservative because we do not explicitly factor in multiple measurements per participant during both baseline and outcome timepoints (e.g. participants will be asked to complete two Intake24 measurements during baseline, and will be asked to wear the wearable device every day). We have chosen to not factor this in due to the uncertainty around compliance with the Intake24 and daily wearing of the wearable devices.

Appendix C - Recommended dietary intake according to the Recommended dietary intake according to the Government Dietary Recommendations

Outcome	Current intake	Desired change
Carbohydrates	212 g/day	Increase
Free sugars	51 g/day	Reduce
Total Fat	69 g/day	Met
Saturated fat	25 g/day	Reduce
Fibre	18 g/day	Increase
Salt (Sodium)	5 g/day (Sodium 1985 mg/day)	Reduce
Fruit and vegetables	297 g/day	Increase
Red and processed meat	52 g/day	Reduce

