2.4 Sample size and minimum detectable size

2.4.1 Summary

The trial will adopt **a household-level randomisation**, with a target sample size of **around 4,200 participants** (2,100 in the control arm, 700 per intervention arm) at the final data collection point (**5 months after the randomisation**) to be powered to detect effect sizes deemed substantive from previous literature (see Section 2.4.2.2 Table 5). We expect users to come from ~2,300 households based on the demographic profile of Wolverhampton LA (see Appendix B).

To achieve a post-attrition sample of 4,200 participants, HUL expects to recruit a sample of around **25,800 participants** at the beginning of the baseline stage, given the attrition rate at various trial stages estimated by HUL (see Section 2.4.2.3 Table 6).

BIT has conducted power calculations for the primary research question "Does the incentive scheme improve physical activity (PA) and diet at the five month mark?". The power calculations focus on the primary outcomes. The primary analysis pools all the treatment arms together and assesses their overall difference against the control.

Given the post-attrition sample size of 4,200 participants, the minimum effect sizes we are powered (at 80% level) to detect at the 5-month's mark in the primary analysis are:

Physical activity primary outcomes:

- Daily MVPA (min/day): 2.4 min/day
- Daily steps: 371 steps/day

Dietary primary outcomes:

- Fruit and vegetables (g/day): 18.7 g/day
- Fibre (g/day): 0.74 g/day
- Free sugars (% food energy): 0.63%
- Saturated Fat (% food energy): 0.31%

The following subsections provide details on the key assumptions and decisions made concerning the power calculation. First, we provide the minimum required sample size at the analysis stage (post-attrition) given the target effect sizes for the primary outcomes (see Table 5). Then, we show the minimum required sample size at the recruitment stage (pre-attrition) given the predicted attrition rate at various stages (see Table 6) based on HUL's estimations. Last, we calculate the minimum detectable effect size for primary outcomes (see Table 7) based on the target sample size confirmed as feasible for this project by HUL and DHSC.

For further information on specific assumptions behind household-level randomisation, multiple-comparisons-adjustment, inclusion of covariates, and allocation ratio among trial arms, please see Appendix B.

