Standard deviation data source	n = 19,898 UK users, whose demographic and obesity profiles are most similar to the target population of this trial ⁴² (HeadUp Labs, 2019)		n = 475 UK adults (19-64 years old) ⁴³ (National Diet and Nutrition Survey 2020)			
Standard deviation estimate	26 min/day	4,096/day	190 g/day	7.5 g/day	6.3 %	3.2 %
Effect size range from prior literature	0.02 to 0.4 SD units ⁴⁴		0.04 to 0.58 SD units ⁴⁵			
Target minimum detectable effect size in SD (MDES)	0.2 SD units		0.11 SD unit			
Target MDES in absolute terms (note: these are all larger than the effect size we estimate to be powered for)	5.2 MVPA min/day	819 steps/day	21 g/day	0.83 g/day	0.69 %	0.35 %
Assumed attrition rate	See Table 7 (Section 2.4.2.3)					

⁴² We only included user whose age profile matches that of the target population, i.e. 18-65 years old, and 69% of the included users were overweight or obese, highly comparable to the proportion in Wolverhampton, which is 70% according to the UK's latest obesity statistics report.

⁴³ Public Health England. (2021). National Diet and Nutrition Survey: Diet, nutrition and physical activity in 2020 - a follow-up study during COVID-19. Retrieved from https://www.gov.uk/government/statistics/ndns-diet-and-physical-activity-a-follow-up-study-during-covid-19

⁴⁴ Mitchell et al. (2020). Financial incentives for physical activity in adults: systematic review and meta-analysis. *British Journal of Sports Medicine*, 54(21), 1259-1268.

⁴⁵ Pomerleau, J., Lock, K., Knai, C., & McKee, M. (2005). Interventions Designed to Increase Adult Fruit and Vegetable Intake Can Be Effective: A Systematic Review of the Literature. *The Journal of Nutrition*, *135*(10), 2486–2495. doi: 10.1093/jn/135.10.2486

Adjustment for baseline covariates	Corr. coef = 0.25-0.75 (0.5 as most realistic)			
Target power	80%			
Adjusting for multiple comparisons	Bonferroni adjustment ⁴⁶ for primary outcomes by category (one comparison each of all incentive arms [pooled] vs. control; the number of adjustments is 2 for PA activities and 4 for dietary outcomes)			
Allocation ratio across arms post-attrition	3 participants in the control arm for every 1 participant in each intervention arm			
Cluster size assumptions for household-level randomisation	Sample will comprise: 39% 1-adult HHs, 41% 2-adult HHs, and 20% 3-adult HHs, with all adults in a HH signing up			
Assumed ICC (more details in Appendix B)	0.2-0.5 (0.2-0.4 as more realistic)			

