2.4.2.2 Minimum required sample size at the analysis stage

Given the target effect size for PA and dietary outcomes, and under the assumptions of household ICC of 0.3, a baseline covariate correlation coefficient of 0.5, we estimate that achieving the targeted MDES requires a post-attrition sample size of **4,200 users (2,100** in the control arm, **700** per intervention arm) at the final data collection point, i.e. 5 months after the randomisation (see Table 6 for details).

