2.4.2.4 Minimum detectable effect size given the sample size at analysis stage

With the sample size at the final data collection point (i.e. post-attrition, n = 4,200), we present the minimum effects we are powered (at 80% level) to detect for six primary outcomes among the trial participants in Table 7, which also provides corresponding benchmarks to interpret those effect sizes.

Table 7. Minimum detectable effect size for primary outcomes given a post-attrition sample size of 4,200

Prima	ry outcomes	MDES	MDES as % of min. (or max.) recommended intake
PA	Daily MVPA (min/day)	2.4 min/day	~ 10% (150 min/week, according to the UK CMO's Physical Activity Guidelines)
	Daily steps	371 steps/day	~ 4% (8,000 steps/day, according to the UK CMO's Physical Activity Guidelines)
Diet	Fruit and vegetables (g/day)	18.7 g/day	~ 5% (~ a quarter of a F&V portion)
	Fibre (g/day)	0.74 g/day	~ 2.5% (~ a third of an apple)
	Free sugars (% food energy)	0.63%	~ 13% of the upper limit of % food energy intake (≤5% food energy)
	Saturated Fat (% food energy)	0.31%	~ 2.8% of the upper limit of % food energy intake (≤11% food energy)

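### Two separate errors in the power section: household percentages are applied to participants, so Table 7's detectable effects do not follow from the stated inputs and household mix; and those inputs do not require 4,200

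*Protocol*

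**What the plan says.** Table 25 in Appendix B gives the census distribution of adults per household in Wolverhampton as 39%, 41% and 20% of 102,177 households with one, two and three or more adults. Table 5 (section 2.4.2.1) repeats these as household shares, with all adults in a household signing up.

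The Appendix B text uses the same percentages for people: "in a sample of 1000 participants, we assume that 39% will come from single-person households" (389 people), with 409 people from two-adult and 202 from three-adult households. From this comes the statement "We estimate that 60% of trial participants could be in the same household with at least another trial participant", which is labelled conservative. Section 2.4.1, on the other hand, says "We expect users to come from ~2,300 households based on the demographic profile" for a sample of 4,200.

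For the sample size, section 2.4.2.2 works "under the assumptions of household ICC of 0.3, a baseline covariate correlation coefficient of 0.5", and says "we estimate that achieving the targeted MDES requires a post-attrition sample size of" 4,200. Section 2.4.2.4 and Table 7 then give "the minimum effects we are powered (at 80% level) to detect for six primary outcomes" at that sample size, without stating the ICC, correlation or alpha used.

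**The concern.** A percentage of households is not a percentage of people. If every adult joins, a three-adult household contributes three participants and a one-adult household contributes one. Using household shares as participant shares therefore overstates the number of people living alone and understates clustering. The document also uses both readings, in different places.

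The detectable effects in section 2.4.1 and Table 7 are what a reader will use to judge what a null result rules out. The figure of 4,200 drives the recruitment target. It also drives the rule in Table 2 for moving the focus to three months, which I read as 80% of 4,200 = 3,360. Both figures should follow from the inputs printed beside them.

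**Working it through.** **Inputs.** ICC 0.3 and r = 0.5, so variance factor 1 - 0.5² = 0.75 (section 2.4.2.2). Power 80%. Bonferroni by category: "the number of adjustments is 2 for PA activities and 4 for dietary outcomes". The overall alpha is not stated; I assume two-sided 5%, giving 0.025 for physical activity and 0.0125 for diet. Analysis groups are 2,100 control and 3 × 700 = 2,100 pooled. SDs are from Table 5 (steps 4,096; MVPA 26; fruit and vegetables 190; fibre 7.5; free sugars 6.3; saturated fat 3.2).

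**Household mix.** Adults = 39,777 + 2 × 41,784 + 3 × 20,616 = 185,193, or 1.812 per household.
- Participant shares: 39,777/185,193 = 21.5%; 83,568/185,193 = 45.1%; 61,848/185,193 = 33.4%.
- Sharing a household: 100 - 21.5 = 78.5%.
- Households for 4,200 people: 4,200/1.812 = about 2,317 on the household reading. On the participant reading it is about 2,776. Only the first fits the stated figure of about 2,300.

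**Design effect (DE) at ICC 0.3,** by two formulas:
- (a) effective sample size, 1/Σ[p_m/(1 + (m - 1) × 0.3)]. Participant mix: 1/(0.389 + 0.409/1.3 + 0.202/1.6) = 1.205. Household mix: 1/(0.2148 + 0.4512/1.3 + 0.3340/1.6) = 1.298.
- (b) person-weighted mean cluster size, 1 + (mean - 1) × 0.3. Participant mix: 1 + 0.813 × 0.3 = 1.244. Household mix: 1 + 1.119 × 0.3 = 1.336.

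**Detectable effect at 4,200** = (z for alpha + 0.8416) × SD × √(DE × 0.75 × 2/2,100), with z = 2.2414 (activity) or 2.4977 (diet).

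Reproducing the plan first, with the participant mix and (a): √(1.205 × 0.75 × 2/2,100) = 0.02934. Steps: 3.083 × 0.02934 × 4,096 = 370.5 (stated 371). Fruit and vegetables: 3.339 × 0.02934 × 190 = 18.6 (stated 18.7). All six outcomes agree within about 2%.

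| Outcome | Table 7 | Participant mix (a) | Household mix (a)-(b) | Target (Table 5) |
|---|---|---|---|---|
| MVPA, min/day | 2.4 | 2.35 | 2.44-2.48 | 5.2 |
| Steps/day | 371 | 370.5 | 384-390 | 819 |
| Fruit and vegetables, g/day | 18.7 | 18.6 | 19.3-19.6 | 21 |
| Fibre, g/day | 0.74 | 0.735 | 0.76-0.77 | 0.83 |
| Free sugars, % | 0.63 | 0.617 | 0.64-0.65 | 0.69 |
| Saturated fat, % | 0.31 | 0.313 | about 0.33 | 0.35 |

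With the household mix, power at 18.7 g/day is about 77% (a) or 75% (b).

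The household mix at **ICC 0.2** gives DE 1.206, 370.6 steps and 18.6 g by (a), so it reproduces Table 7 equally well.

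**Sample size for 0.11 SD.** Per group without clustering: 2 × 0.75 × 3.339²/0.11² = 1,382, so 2,765 in total. Multiplied by DE:
- participant mix: 3,331 (a) to 3,439 (b);
- household mix: 3,588 (a) to 3,693 (b).

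At ICC 0.3 and alpha 0.0125, a figure near 4,200 appears only with r = 0.25 and the participant mix (4,164-4,298). With the stated inputs and the household mix, 4,200 gives about 87% (a) or 86% (b) power for 0.11 SD.

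**The case against.** **The source of Table 7 is not proven.** A reader might infer that Table 7 was computed from the wrong mix. The document does not show this. The household mix at ICC 0.2, which lies within Table 5's range, gives the same values. The simple formula using the mean household size of 1.812 gives DE 1.244 at ICC 0.3: 376 steps and 18.9 g, but also 2.39 min and 0.627%, which match the stated 2.4 and 0.63. This stands as a limit on attribution. It does not remove the conflict, because 0.3 is the only single ICC stated and the household mix does not return 371 steps or 18.7 g at that value.

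**78.5% is an upper figure.** It needs every adult to join and to be present at analysis. Footnote 48 says not all members must sign up, footnote 91 expects smaller households, and Table 6 expects 62-78% attrition by five months. If presence were independent within households (an assumption), 70% present would give 62% sharing and a DE of 1.20, close to the plan's; at 4,200/15,500 = 27% present it would be 28% and 1.07. Dropout is likely to be correlated within households, so the truth may lie between. So 60% could still prove cautious for the analysed sample. But the plan does not argue this: it assumes full sign-up, and its figure of about 2,300 households applies full households to the 4,200. Relative to those assumptions, 60% is too low.

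**The size is small and there is other margin.** Footnote 93 leaves repeated measures out. Footnote 46 notes that Bonferroni is stricter than the planned Benjamini-Hochberg procedure. Appendix B expects a correlation near 0.8 for MVPA but uses 0.5. Section 2.4.1 already calls the target size confirmed as feasible, and Table 5 notes that the targets exceed the detectable effects. All of this stands, and it keeps the point to a correction of stated figures.

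**The two errors should not be linked.** It is tempting to say that 4,200 is wrong because of the household slip, or that the trial is underpowered. Neither follows. The participant mix already gives only 3,330-3,440, and correcting the mix moves the requirement closer to 4,200.

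**Conclusion.** Both errors hold, separately.

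1. Appendix B treats household shares as participant shares, contradicting Tables 5 and 25 and the household count in section 2.4.1. At ICC 0.3 and r = 0.5, the household mix puts most detectable effects about 3-5% above Table 7; MVPA barely moves. Table 7 therefore conflicts with either the household mix or the stated ICC. This rests on two-sided 5% alpha, full sign-up and design effect formula (a) or (b).

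2. The inputs in section 2.4.2.2 do not require 4,200. The mismatch is a surplus of about 500-600 on the household mix (4,200 - 3,693 = 507; 4,200 - 3,588 = 612).

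No conclusion about the adequacy of 4,200 changes. The margin is thinner at the three-month fallback line: 3,360 lies below the household-mix requirement and gives about 75-77% power for 0.11 SD.

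**What to change.** - **Appendix B:** give the participant shares as 21.5/45.1/33.4%; replace 60% with 78.5%, stated as an upper figure that holds under full sign-up; drop the conservative label for the 60%. Correct the worked example of 1,000 participants so that it agrees with Tables 5 and 25 and with the roughly 2,300 households in section 2.4.1.
- **Section 2.4.1 and Table 7:** state the ICC, baseline correlation, alpha and design effect formula used, and restate the detectable effects from them.
- **Section 2.4.2.2 and Table 5:** give about 3,600-3,700 as the requirement for 0.11 SD under the stated inputs and describe 4,200 as the agreed target with margin, or give the inputs that produce 4,200.

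The cost is a recalculation and edited text. No extra participants and no change to the design are needed.
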